1. MEDICAL MONITOR/SPONSOR INFORMATION PAGE						
Role	Name	Day Time Phone Number and email address	After-hours Phone/Cell/ Pager Number	Fax Number	Site Address	
Primary Medical Monitor	PPD			n/a	GSK [name]	
Secondary Medical Monitor				n/a	GSK Upper Providence, PA, USA	
SAE contact information	Medical monitor as above					

Change	Section, Text affected, and Rationale	PPD	n/a	GSK [name]
	Clinical Investiga tion Lead - CIL			
	Operatio ns & Science Lead- OSL			
	Data Manager Lead			
2.	
Section 1: Protocol Synopsis for Study MEA115921, Overall Design, paragraph 6.
 
Section 4.1: Overall Design, paragraph 6.
 
Added:
 
UK only Clarification: Eligible subjects can continue to receive mepolizumab under this LAP until July 2022 or until the Sponsor discontinues development in EGPA or until the subject meets any of the withdrawal/stopping criteria.
 
Rationale: Clarification requested by the UK regulatory authority.
			
3.	
Section 5.3: Withdrawal/Stopping Criteria, paragraph 2, bullet 5.
 
Section 5.4: Subject and Study Completion, paragraph 1
 
Added:
 
UK only clarification: Eligible subjects can continue to receive mepolizumab under this LAP until July 2022.
 
Rationale: Clarification requested by the UK regulatory authority.
			
4.	
Appendix 5 – Country Specific Requirements
			

Chan	Section, Text affected, and Rationale
ge	
Added:
 
UK only clarification: Eligible subjects can continue to receive mepolizumab under this LAP until July 2022.

**Description:**

The purpose of this RAP is to describe the planned analyses and output to be included in the Clinical Study Report for the Long-term Access Programme (LAP) for mepolizumab in EGPA. The LAP comprises a clinical trial (MEA116841) and compassionate use programme (201607). Planned outputs also include periodic interim analyses conducted after the effective date of this RAP, as necessary.

## 1. INTRODUCTION

The purpose of this reporting and analysis plan (RAP) is to describe the analyses and planned outputs to be included in the Clinical Study Report for the Long-term Access Programme (LAP) for mepolizumab in EGPA. The LAP comprises a clinical trial (MEA116841) and compassionate use programme (201607). This document also describes the planned outputs to be included in periodic interim analyses, conducted after the effective date of this RAP, as appropriate

This RAP is based on MEA116841 study protocol amendment 4 issued 18-Jun-2019 (GlaxoSmithKline Document Number [2014N201870\\_04](#)) and has been amended following the previous RAP version which has been used to provide the analyses required for the previous Interim Clinical Study Report (ICSRs).

The clinical data base for the LAP consists of the following subjects:

- Subjects recruited into study MEA116841
- Subjects recruited as part of the named patient supply guidance program 201607

Available data from the above subjects will be included in the analyses specified in this RAP. Combined summaries will be produced from the clinical trial data base for MEA116841 and the NPS guidance program.

### 1.1. RAP Amendments

All revisions since the previous approved RAP (dated 26-Sep-2016) are listed below:

RAP Section	Amendment Details
All	Formatting changes to fit RAP_Template_Master_v2 (8-Aug-2017)
3.1 Interim Analyses	Details of previous interim analysis (5-Sep-2016 cut-off date) were added
4.1 Protocol Deviations	Reference added to updated PDMP
7.1 Safety Analyses	Added text providing additional information regarding adverse event reporting for MEA116841 and 201607
9.7.4 Study Population Tables	
 
• Removed “Summary of Reasons for Screen and Run-In Failure” (Rationale: there was only one occurrence and these data are included in the listings)
 
• Removed “Summary of Inclusion/Exclusion Criteria” (Rationale: there was only one occurrence and these data are included in the listings)
 
• Added “Summary of Age Ranges” (Required as per revised RAP template)
 
• Added “Summary of Serious Adverse Events by System Organ Class and Preferred Term (Number of Participants and Occurrences)” (Required for disclosure purposes).
 

RAP Section	Amendment Details
	

• Added “Summary of Non-Serious Drug-Related Adverse Events by Overall Frequency” (Required for Plain language Summaries)

• Added “Summary of Non-Serious Drug-Related Adverse Events by Overall Frequency” (Required for Plain language Summaries)

## 2. SUMMARY OF KEY PROTOCOL INFORMATION

### 2.1. Changes to the Protocol Defined Statistical Analysis Plan

There were no changes or deviations to the originally planned statistical analysis specified in the protocol.

### 2.2. Study Objective(s) and Endpoint(s)

Objective	Endpoints
The objective of this protocol is to provide a mechanism to supply mepolizumab on an individual subject basis to eligible subjects who previously participated in GSK sponsored study MEA115921.	N/A

## 2.3. Study Design

Overview of Study Design and Key Features	
<pre> graph TD     A[Submit Application Form to GSK (on agreement with patient information will be shared with GSK)] --> B[GSK Physician confirms eligibility]     B --> C[Subject provided Informed Consent]     C --> D[Mepolizumab Treatment 300 mg SC every 4 weeks Continues if appropriate benefit:risk and until either i) marketed product available or ii) GSK discontinues the programme or iii) any of the withdrawal/stopping criteria are met]     D --> E[Safety Follow-up: Prior to the start of use of marketed product or 12 weeks after the last dose]   </pre>	
Design Features	See figure above.
Dosing	Eligible subjects will receive subcutaneously administered mepolizumab at a dose of 300 mg SC every 4 weeks.
Treatment Assignment	All eligible subjects will receive mepolizumab as described above.

## 2.4. Statistical Hypotheses / Statistical Analyses

No statistical hypotheses are defined for this study.

### 3. PLANNED ANALYSES

#### 3.1. Interim Analyses

A summary of integrated safety data from MEA116841 and 201607 (compassionate use programme) was conducted to support mepolizumab EGPA submissions in the US and Japan, using a cut-off date of 05-SEP-2016 (GlaxoSmithKline Document Number: [2017N320079\\_00](#)).

Further interim analyses may be conducted, as required.

This RAP contains details of analyses proposed for future interim analyses as well as the final study report. Access to the results from such interim analyses will not be confidential. Specifically the results will be provided to the study team and GSK governance boards, and may be provided to external investigators and to regulatory authorities.

#### 3.2. Final Analyses

The final planned primary analyses will be performed after the completion of the following sequential steps:

1. All participants have completed the study as defined in the protocol
2. All required database cleaning activities have been completed and final database release (DBR) and database freeze (DBF) has been declared by Data Management.

### 4. ANALYSIS POPULATIONS

Population	Definition / Criteria	Analyses Evaluated
All Subjects Enrolled	Comprises all subjects enrolled and for whom a record exists on the study database. This population will be used for summarising reasons for screen and run-in failures.	Study Population
Safety	Comprise of all subjects who receive at least one dose of mepolizumab	
 
• Study Population
 
• Safety
 

#### 4.1. Protocol Deviations

Important protocol deviations (including deviations related to study inclusion/exclusion criteria, failure to report pregnancy and SAEs and informed consent) will be summarised and listed.

Protocol deviations will be tracked by the study team throughout the conduct of the study in accordance with the Protocol Deviation Management Plan [version 5.0, 05-June-2019].

- Data will be reviewed prior to freezing the database to ensure all important deviations are captured and categorised on the protocol deviations dataset.

- This dataset will be the basis for the summaries and listings of protocol deviations.

A separate summary and listing of all inclusion/exclusion criteria deviations will also be provided. This summary will be based on data as recorded on the inclusion/exclusion page of the eCRF.

## 5. CONSIDERATIONS FOR DATA ANALYSES AND DATA HANDLING CONVENTIONS

### 5.1. Study Treatment and Subgroup Display Descriptors

Summaries will be presented for all subjects receiving open-label mepolizumab. In addition, summaries will also be presented by the actual treatment the participant received in the randomised double-blind study (MEA115921).

Treatment group descriptors will be assigned as follows:

Treatment Group Descriptions			
RandAll NG from Study MEA115921		Data Displays for Reporting	
Code	Description	Description	Order [1]
P	Placebo	300mg SC Prev. Placebo	1
A	Mepolizumab 300mg SC	300mg SC Prev. Mepo	2
N/A	N/A	300mg SC Total	3

### 5.2. Examination of Subgroups

The following subgroups are defined for this study:

Subgroups
Age group: 
 
<65 years
 
≥65 years
 

Sex 
 
Male
 
Female
 

Race 
 
African American/African Heritage
 
White
 
Asian
 
Other
 

### 5.3. Other Considerations for Data Analyses and Data Handling Conventions

Other considerations for data analyses and data handling conventions are outlined in the appendices:

Section	Component
9.2	Appendix 2: Study Phases and Treatment Emergent Adverse Events
9.3	Appendix 3: Data Display Standards & Handling Conventions
9.4	Appendix 4: Derived and Transformed Data
9.5	Appendix 5: Reporting Standards for Missing Data

## 6. STUDY POPULATION ANALYSES

### 6.1. Overview of Planned Study Population Analyses

The study population analyses will be based on the Safety population.

Study population analyses including analyses of subject's disposition, protocol deviations, demographic and baseline characteristics, prior and concomitant medications, and exposure and treatment compliance will be based on GSK Core Data Standards. Details of the planned displays are presented in [Appendix 7: List of Data Displays](#).

## 7. SAFETY ANALYSES

The safety analyses will be based on the Safety population, unless otherwise specified.

The LAP comprises a clinical trial (MEA116841) and compassionate use programme (201607) restricted to subjects who participated in MEA115921. The compassionate use programme (CUP) was conducted under a guidance document which mirrored the objectives of MEA116841. Since 201607 was run as a CUP, the treating physician was the responsible party. Per local legal requirements, serious adverse event reporting was required at a minimum. Furthermore, GSK did not monitor CUP 201607, and therefore verification that all non-serious adverse events (AEs) were reported is not possible.

For this reason, summaries of adverse events are reported separately for MEA116841 and 201607, with the exception of serious adverse events, which are additionally reported using combined MEA116841 and 201607 data.

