### 9.5.2. Handling of Missing Data

Element	Reporting Detail
General	
 
Missing data occurs when any requested data is not provided, leading to blank fields on the collection instrument : 
 
These data will be indicated by the use of a "blank" in subject listing displays. Unless all data for a specific visit are missing in which case the data is excluded from the table.
 
Answers such as "Not applicable" and "Not evaluable" are not considered to be missing data and should be displayed as such.
 
 
 

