3.40.	Safety	mid_mepo_egpa_lap /interim1 Table 3.36	Summary Profile of On-Treatment Adverse Events of Special Interest: Serious Cardiac, Vascular and Thromboembolic	
 
• MEA116841
 
• 201607
 
	IA , SAC
3.41.	Safety	mid_mepo_egpa_lap /interim1 Table 3.37	Summary Profile of On-Treatment Adverse Events of Special Interest: Serious Ischemic Events	
 
• MEA116841
 
• 201607
 
	IA , SAC

Safety: Tables					
No.	Population	IDSL / Example Shell	Title	Programming Notes	Deliverable [Priority]
Exposure-Adjusted Adverse Events					
3.42.	Safety	mid_mepo_egpa_lap /interim1 Table 3.38	Summary of Exposure Adjusted On-Treatment Adverse Events	
 
• MEA116841
 
• 201607
 
	IA , SAC
3.43.	Safety	mid_mepo_egpa_lap /interim1 Table 3.39	Summary of Exposure Adjusted Most Frequent On-Treatment Adverse Events Reported by 3% or More Subjects In Any Treatment Group	
 
• MEA116841
 
• 201607
 
	IA , SAC
3.44.	Safety	mid_mepo_egpa_lap /interim1 Table 3.40	Summary of Exposure Adjusted Drug Related Adverse Events	
 
• MEA116841
 
• 201607
 
	IA , SAC
3.45.	Safety	mid_mepo_egpa_lap /interim1 Table 3.41	Summary of Exposure Adjusted On-Treatment Adverse Events Leading To Permanent Discontinuation of Study Drug or Withdrawal From Study	
 
• MEA116841
 
• 201607
 
	IA , SAC
3.46.	Safety	mid_mepo_egpa_lap /interim1 Table 3.42	Summary of Exposure Adjusted On-Treatment Serious Adverse Events	
 
• MEA116841
 
• 201607
 
	IA , SAC
3.47.	Safety	mid_mepo_egpa_lap /interim1 Table 3.43	Summary of On-Treatment Adverse Events by Age Category	
 
• MEA116841
 
• 201607
 
	IA , SAC
3.48.	Safety	mid_mepo_egpa_lap /interim1 Table 3.44	Summary of On-Treatment Adverse Events by Sex	
 
• MEA116841
 
• 201607
 
	IA , SAC
3.49.	Safety	mid_mepo_egpa_lap /interim1 Table 3.45	Summary of On-Treatment Adverse Events by Race	
 
• MEA116841
 
• 201607201607
 
	IA , SAC

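### Non-serious AE figures for 201607 are at best minimum reported frequencies, yet the SAP plans them as percentages, rates and subgroup summaries, and combines them with the trial's in Tables 3.18 and 3.20

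*SAP*

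**What the plan says.** SAP section 7 describes 201607 as a compassionate use programme for which the treating physician was responsible, "conducted under a guidance document which mirrored the objectives of MEA116841". On what had to be reported it says: "Per local legal requirements, serious adverse event reporting was required at a minimum". It then concedes that "GSK did not monitor CUP 201607, and therefore verification that all non-serious adverse events (AEs) were reported is not possible". The stated response is that "summaries of adverse events are reported separately for MEA116841 and 201607, with the exception of serious adverse events", which are also shown combined.

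The displays are set elsewhere in the SAP:

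- **Denominator.** The Safety population in section 4 is "Comprise of all subjects who receive at least one dose of mepolizumab". It is not restricted to subjects whose AE reporting is known to be complete.
- **Statistics.** Section 9.3.2 asks for counts and percentages for categorical data. Section 9.4.2 counts exposure from first dose to last dose with 29 days added, adjusted for treatment breaks.
- **Missing data.** Section 9.5.2 says "Missing data occurs when any requested data is not provided, leading to blank fields on the collection instrument". There is no rule for an event that was never entered.
- **Tables.** Section 9.7.5 lists 201607 for the general AE tables, the special-interest tables, the exposure-adjusted tables (3.42 is titled "Summary of Exposure Adjusted On-Treatment Adverse Events") and the subgroup tables (3.47 is titled "Summary of On-Treatment Adverse Events by Age Category").

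**The concern.** Showing the two programmes apart stops an uncertain count from entering the trial's figures. It does not make the uncertain count valid as an incidence. Printed in the same format as MEA116841, a 201607 percentage or rate invites comparison with the trial, and a low figure may reflect low risk, incomplete reporting or both. Exposure adjustment makes this worse, because dividing by person-time suggests a precision that the numerator does not have.

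The figures will have readers. Protocol section 9.1 says interim analyses are meant to inform the benefit-risk assessment in EGPA. SAP section 3.1 says interim results are not confidential and may go to external investigators and regulators. Table 3.18, which combines the programmes, is marked as needed for the Plain Language Summary. Missed events can only lower a frequency, so any error is in the drug's favour.

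**Working it through.** Neither document gives a sample size, event count, person-time or reporting completeness for 201607, so there is no planned figure to reproduce. The check traces the displays and then shows how incomplete reporting would act on each kind of statistic.

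**1. Which tables are affected.** Tables that list 201607 and can include non-serious events:

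- 3.3 to 3.9: 7
- 3.21 to 3.30: 10
- 3.34 to 3.39: 6
- 3.42 to 3.45: 4
- 3.47 to 3.49: 3

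7 + 10 + 6 + 4 + 3 = 30 of the 49 safety tables. This is an upper count. Some special-interest categories may be mostly serious: the two malignancy tables (3.30 and 3.39) are an example, since Protocol section 12.4.2 gives malignant cancers as an example of a serious event. Tables 3.31 to 3.33, 3.40, 3.41 and 3.46 cover serious events only and are not counted.

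**2. Does the separation hold?** Section 7 combines only SAEs. Table 3.18 covers non-serious drug-related AEs, and its programming notes list the two programmes combined. Table 3.20 covers all investigator-reported cardiovascular events. It is also combined, and Protocol section 12.4.3 collects those events whether serious or not. These two come on top of the 30.

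**3. Effect of incomplete reporting.** Let c be the fraction of non-serious AEs reported in 201607. The documents do not give c, so 100% to 25% is an assumed range. They do not rule out 100%.

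- Event rate: reported = c × true.
- Subjects with at least one AE: 1 − exp(−c × m), where m is the mean number of true AEs per subject, events are Poisson and each is reported independently.
- True incidence needed to reach the 3% cut-off for common AEs, for an event occurring at most once per subject: 3% / c.

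| c | Rate shown if truth is 1000 per 1000 person-years | Subjects with any AE, m = 1 | Subjects with any AE, m = 3 | True incidence needed to reach 3% |
|---|---|---|---|---|
| 100% | 1000 | 63.2% | 95.0% | 3% |
| 75% | 750 | 52.8% | 89.5% | 4% |
| 50% | 500 | 39.3% | 77.7% | 6% |
| 25% | 250 | 22.1% | 52.8% | 12% |

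Percentages of subjects fall less than rates when missed events are scattered. At m = 3 and c = 75% the relative drop is (95.0 − 89.5) / 95.0 = 5.8%, against 25% for the rate. The rate column applies to non-serious events alone. If a share s of all events is serious and fully reported, the all-AE rate is shown at s + (1 − s)c of its true value.

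**4. Subgroups.** With a true rate ratio of 1, the reported ratio is c1 / c2. Equal completeness gives 1.0. Completeness of 75% against 50% gives 0.75 / 0.50 = 1.5, and 75% against 25% gives 3.0.

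**5. Combined display.** If 201607 contributes a share w of person-time and true rates are equal, the pooled rate is 1 − w(1 − c) of the truth. At w = 10% and c = 75% this is 97.5%. At w = 50% and c = 25% it is 62.5%. Both w and c are assumptions.

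**The case against.** The SAP discloses the limitation, explains it and responds on purpose: its amendment list in section 1.1 records the added text on AE reporting in the two programmes. It defines no hypotheses (section 2.4), and Protocol section 9 promises only to summarise what is reported. On that view a caveat is enough, and suppressing percentages is a matter of taste. The programming notes for Tables 3.7 to 3.9 already allow a listing when events are few. Several tables follow earlier interim shells that are not in the documents and may carry footnotes. A reader can also recompute percentages from the population counts in Table 1.5.

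Part of this stands. The analysis is descriptive, and the footnote matters more than hiding a percentage. But disclosure in section 7 does not travel with a table, and no visible programming note carries the caveat. Tables 3.18 and 3.20 also show that the chosen response is not applied throughout.

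Three stronger readings are tempting, and the documents do not support them:

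- A reader might infer that non-serious reporting was not required in 201607. The SAP says only that SAEs were the minimum under local law. What the guidance document asked for is not stated.
- A reader might infer that the age, sex and race summaries are confounded by who reported. Nothing shows that completeness differed between subgroups, and equal under-reporting leaves ratios unchanged. Distortion is possible but not shown.
- A reader might take 25%, 50% or 75% as the size of the understatement. Those figures follow from assumed completeness and apply to non-serious event rates, not directly to percentages of subjects or to rates that include SAEs.

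**Conclusion.** The point holds in a limited form. By the SAP's own account, completeness of non-serious AEs in 201607 cannot be verified, so percentages and exposure-adjusted rates over all dosed subjects and full exposure are at best minimum reported frequencies. That unreported events count as zero is the arithmetic result of the denominator and the missing-data rule, not something the SAP states. Any bias is downward, and its size cannot be determined from the documents; it is nil if reporting was complete. Subgroup differences may be distorted if completeness differed between subgroups. Separate display does not repair the 201607 figures. For Table 3.18, and for the non-serious events in Table 3.20, the combined display departs from the rule in section 7. Nothing here affects the tables restricted to SAEs, for which reporting was required. This is a cheap improvement, not a threat to the trial's own separately displayed results.

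**What to change.** Edit SAP Appendix 7 as follows:

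1. Remove 201607 from the exposure-adjusted Tables 3.42 to 3.45. Keep it in Table 3.46, which covers SAEs.
2. In Tables 3.47 to 3.49, limit 201607 to SAEs, so that its serious events are not lost from the subgroup displays.
3. In the remaining 201607 tables that include non-serious AEs, show counts of reported events with the footnote *completeness of non-serious AE reporting not verified; minimum reported frequency*. In Tables 3.5 and 3.8, replace the 3% selection for 201607 with all reported events or a listing, since the cut-off has no meaning without a valid percentage.
4. Remove the combined display from Table 3.18 and from the non-serious part of Table 3.20.

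Keep all SAE tables and Listing 11 for 201607, so every reported event remains visible. The cost is table-list edits and footnotes. The loss is the 201607 non-serious percentages and rates, and its non-serious AEs by subgroup.

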### 7.1. Adverse Events

Adverse events will be coded using the Medical Dictionary for Regulatory Activities (MedDRA) coding dictionary. Classification of an AE as pre-, on- or post-treatment will be made with reference to the study treatment start and stop date/time and the AE onset date/time. If the AE onset date is missing or partial then the AE will be considered on-treatment unless there is evidence to the contrary (e.g. the month of the onset date is present and is less than the month of the first dose of study medication). AEs with onset up to 4 weeks after the last dose of treatment will be considered on-treatment. AEs with onset after this period will be considered post-treatment but will be assigned to the treatment previously received.

Any SAEs for screen failures, run-in failures or subjects who were enrolled but did not receive treatment will be classified as pre-treatment SAEs.

The most frequent on-treatment AEs will be defined as AEs with frequency  $\geq 3\%$  in any treatment group.

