Serious and Other Significant Adverse Events					
3.10.	Safety	AE1	Summary of Pre-Treatment Serious Adverse Events by System Organ Class and Preferred Term	
 
MEA116841
 
201607For studies with few events/participants listing is sufficient: discuss this option with your disclosure representative.
 
MEA116841 + 201607
 
	IA , SAC

Safety: Tables					
No.	Population	IDSL / Example Shell	Title	Programming Notes	Deliverable [Priority]
3.11.	Safety	AE1	Summary of On-Treatment Serious Adverse Events by System Organ Class and Preferred Term	
 
MEA116841
 
201607For studies with few events/participants listing is sufficient: discuss this option with your disclosure representative.
 
MEA116841 + 201607
 
	IA , SAC
3.12.	Safety	AE1	Summary of Post-Treatment Serious Adverse Events by System Organ Class and Preferred Term	
 
MEA116841
 
201607For studies with few events/participants listing is sufficient: discuss this option with your disclosure representative.
 
MEA116841 + 201607
 
	IA , SAC
3.13.	Safety	AE16	Summary of Serious Adverse Events by System Organ Class and Preferred Term (Number of Participants and Occurrences)	Required for data disclosure 
 
MEA116841
 
201607For studies with few events/participants listing is sufficient: discuss this option with your disclosure representative.
 
MEA116841 + 201607
 
	IA , SAC

Safety: Tables					
No.	Population	IDSL / Example Shell	Title	Programming Notes	Deliverable [Priority]
3.14.	Safety	AE1	Summary of On-Treatment Non-Fatal Serious Adverse Events by System Organ Class and Preferred Term	
 
MEA116841
 
201607For studies with few events/participants listing is sufficient: discuss this option with your disclosure representative.
 
MEA116841 + 201607
 
	IA , SAC
3.15.	Safety	AE1	Summary of Fatal Serious Adverse Events by System Organ Class and Preferred Term	
 
MEA116841
 
201607For studies with few events/participants listing is sufficient: discuss this option with your disclosure representative.
 
MEA116841 + 201607
 
	IA , SAC

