## CONFIDENTIAL

MEA116841

ICH: Listings					
No.	Population	IDSL / Example Shell	Title	Programming Notes	Deliverable [Priority]
Exposure and Treatment Compliance					
9.	Safety	See mid_mepo_egpa_lap/interim1 Listing 10	Listing of Exposure Data		IA , SAC
10.	Safety	See mid_mepo_egpa_lap/interim1 Listing 26	Listing of Current and Previous Treatment		IA , SAC
Adverse Events					
11.	Safety	AE8	Listing of All Adverse Events		IA , SAC
12.	Safety	AE7	Listing of Subject Numbers for Individual Adverse Events		IA , SAC
13.	Safety	AE2	Listing of Relationship Between Adverse Event System Organ Classes, Preferred Terms, and Verbatim Text		IA , SAC
Serious and Other Significant Adverse Events					
14.	Safety	AE8	Listing of Fatal Serious Adverse Events		IA , SAC
15.	Safety	AE8	Listing of Non-Fatal Serious Adverse Events		IA , SAC
16.	Safety	AE14	Listing of Reasons for Considering as a Serious Adverse Event		IA , SAC
17.	Safety	AE8	Listing of Adverse Events Leading to Withdrawal from Study / Permanent Discontinuation of Study Treatment		IA , SAC
18.	Safety	See mid_mepo_egpa_lap/interim1 Listing 19	Listing of Adverse Events Defined by the Investigator as a Systemic (Non-Allergic or Allergic/Hypersensitivity) Injection Reaction		IA , SAC

ICH: Listings					
No.	Population	IDSL / Example Shell	Title	Programming Notes	Deliverable [Priority]
19.	Safety	See mid_mepo_egpa_lap/interim1 Listing 20	Listing of Adverse Events Defined by the Investigator as a Local Injection Site Reaction		IA , SAC
20.	Safety	See mid_mepo_egpa_lap/interim1 Listing 21	Listing of AEs of Systemic Reactions Meeting Anaphylaxis Criteria		IA , SAC
21.	Safety	See mid_mepo_egpa_lap/interim1 Listing 22	Listing of Potential Opportunistic Infections		IA , SAC
22.	Safety	See mid_mepo_egpa_lap/interim1 Listing 23	Listing of Serious Ischemic AEs		IA , SAC
23.	Safety	See mid_mepo_egpa_lap/interim1 Listing 24	Listing of Malignancies		IA , SAC
Corticosteroid Medication					
24.	Safety	See mid_mepo_egpa_lap/interim1 Listing 11	Listing of Corticosteroid Therapy		IA , SAC

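### SAP 7.1 classes SAEs in never-dosed subjects as pre-treatment SAEs, but every AE and SAE display is restricted to dosed subjects, so these events reach no SAE output

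*SAP*

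**What the plan says.** SAP section 7.1 assigns adverse events to a pre-, on- or post-treatment phase and then adds a rule for people who were never treated: "Any SAEs for screen failures, run-in failures or subjects who were enrolled but did not receive treatment will be classified as pre-treatment SAEs".

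SAP section 4 defines two populations.

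- Safety: "Comprise of all subjects who receive at least one dose of mepolizumab".
- All Subjects Enrolled: everyone enrolled who has a database record. Its stated purpose is "This population will be used for summarising reasons for screen and run-in failures", and its entry under analyses evaluated is Study Population only.

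SAP section 7 sets the default: "The safety analyses will be based on the Safety population, unless otherwise specified".

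SAP Appendix 7 has one table for the pre-treatment class, Table 3.10, "Summary of Pre-Treatment Serious Adverse Events by System Organ Class and Preferred Term", and its population is Safety.

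Protocol section 7.3.1.1 starts general AE and SAE collection at the first dose. SAEs judged related to study participation or to a GSK product are recorded from consent. The Time and Events Table (protocol section 7.1) schedules an AE/SAE review at screening.

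**The concern.** The rule in SAP 7.1 and the display list in Appendix 7 do not meet. The rule applies to people who received no dose, and the display meant for that class admits only people who received one. A programmer must either follow the population label, and drop the event, or follow 7.1, and override the label without instruction. That choice could differ between an interim deliverable and the final one.

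At stake is whether the study report accounts for every SAE that the protocol asks sites to record. The programme tests no hypothesis and its main output is safety displays, so completeness of the SAE record matters more here than it would as a side issue in an efficacy trial. The events concerned are few, but before dosing they are by definition SAEs judged related to participation or to a GSK product, and one could be fatal.

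**Working it through.** No sample size, error rate or event count is involved, and the plan gives no figure to reproduce. The check compares the population column of each display in SAP Appendix 7 with the definitions in SAP section 4.

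1. *Who the rule covers.* Screen failures, run-in failures and enrolled but untreated subjects. None has a dose, so none can be in Safety. All Subjects Enrolled is the only defined population that can contain them.

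2. *Tables (sections 9.7.4 and 9.7.5).* All 49 safety tables, 3.1 to 3.49, are on Safety. Tables 3.1 and 3.2 are exposure tables, which leaves 49 − 2 = 47 AE or SAE tables, all on Safety. Many could not hold a pre-treatment SAE anyway, because their titles limit them to on- or post-treatment or to non-serious events. The ones that matter most are 3.10 (pre-treatment SAEs), 3.13 (SAEs with no phase limit, marked as needed for disclosure) and 3.15 ("Summary of Fatal Serious Adverse Events by System Organ Class and Preferred Term").

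3. *Listings (section 9.7.6).* Listings 3 to 24 are on Safety, 22 of 24. The AE listings are 11 to 23, which is 13 listings, all on Safety. They include Listing 11, "Listing of All Adverse Events", and the fatal and non-fatal SAE listings, 14 and 15.

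4. *Displays on All Subjects Enrolled.* There are five: Tables 1.3 (country and site), 1.5 (study populations) and 1.7 (age ranges), and Listings 1 (reasons for screen failure) and 2 (reasons for study withdrawal). By title, none is an AE or SAE display.

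5. *Result.* AE or SAE displays on Safety: 47 + 13 = 60. AE or SAE displays on All Subjects Enrolled: 0.

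6. *Could data exist?* Yes. Protocol 7.3.1.1 records related SAEs from consent, and screening may last up to 4 weeks. The rationale in SAP section 1.1 for removing the summary of screen and run-in failures mentions a single occurrence, so the undosed group is not purely hypothetical. The documents do not say whether that subject had an SAE.

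7. *How large could it be?* The documents give one occurrence and no SAE rate for undosed subjects. The design flow in SAP section 2.3 puts the sponsor's eligibility confirmation before consent, which should keep the group small. No probability can be derived from these inputs.

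**The case against.** The best defence is the phrase in SAP section 7 that allows exceptions to the Safety default. On this reading, 7.1 itself specifies the exception and sends these SAEs to Table 3.10. In support, the population column is not always literal: Listing 6 is labelled Safety although its note says that it shows screened subjects outside that population. This does not carry the point. The sentence in 7.1 assigns a treatment phase and names no population. Listing 6 has a note that overrides its label, and Table 3.10 has none.

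It can also be said that the sentence looks like template text, since it mentions run-in failures and the Time and Events Table has no run-in. That may be so, but the screen-failure and enrolled-but-untreated parts do fit this protocol.

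Listings 1 and 2 might hint at an SAE that ended participation, depending on the reason recorded. By title they list reasons for screen failure or withdrawal, so they are not SAE records.

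What stands is the limit on scope. Three stronger readings are tempting, and the documents do not support them.

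- *Table 3.10 is empty by design.* It is not. It can show SAEs with onset before the first dose in subjects who were later dosed.
- *A particular set of SAE tables and listings is on the wrong population and should be moved.* Only Table 3.10 is tied to the rule by its wording. Other displays share the limit, for example Listings 12 and 13, and Tables 3.16, 3.17 and 3.19 for drug-related events. Moving some listings and not others would leave the AE listings covering different subjects.
- *SAEs are being missed by the sponsor.* Reporting to the sponsor within 24 hours (protocol 7.3.1.1) and daily SAE review by the medical monitor (protocol 4.1) do not depend on the SAP.

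**Conclusion.** The point holds, and it is minor. It is an internal contradiction and not just missing detail: the SAP defines a class of SAEs, and its own population labels then exclude the untreated part of that class from every AE and SAE display. The effect is confined to completeness of the report. No rate, denominator or comparison in dosed subjects changes.

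The conclusion assumes that the population column in Appendix 7 is applied as printed. The display shells and the sponsor's general reporting standards are not in the documents and might carry a convention for untreated subjects, but nothing in the SAP says so. The documents also do not show that such an SAE has occurred. One screen or run-in failure occurrence is mentioned, and the number of SAEs concerned may be zero.

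**What to change.** Add one listing to SAP section 9.7.6, on All Subjects Enrolled, of SAEs in subjects who received no dose. It should show causality and outcome, and state that there were none if it is empty. Footnote Tables 3.10, 3.13 and 3.15 to this listing. In SAP section 4, add this use to the All Subjects Enrolled row, so that the population table agrees with section 7.1. Leave all existing tables, listings and denominators on Safety.

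The cost is one new listing, three footnotes and one entry in section 4. It needs no new data collection and changes no result in dosed subjects. If there were no such events, the report would say so explicitly.
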